[name] began CIC in 2010 as a pilot project and continues as the Director. Coaching Into Care has grown significantly since 2011 when it became a national program; in 2014 alone, CIC received over 3000 initial (incoming) calls. About 50% concerned a Veteran from the OEF/OIF/OND eras. About 70% of the calls in 2014 concerned psychosocial issues, including mental health, substance abuse, and/or behavioral concerns that may have an impact on the Veterans' or others' physical safety. Seventy-five percent of the callers were female, with 28% of them being a spouse or other intimate partner, 19% parents, 12% were sons, daughters or siblings, 28% were other types of family members, friends or other relationships. Thirteen percent of the calls were directly from Veterans about mental health, benefits, or other concerns. Virtually all of the callers to CIC have internet access; exceptions tend to be older callers and/or those with lower financial resources.

Quality Assurance (QA) data from our call center operations have indicated that the service is highly rated by callers but the impact of the service may be limited, especially in the cases of substance misuse. Within about 3 months of first calling, the treatment engagement of the Veteran who is the subject of the calls with CIC rises modestly [11]. In 939 CSO callers who started coaching since November 2014 whose concerns were specifically focused on mental health problems and no substance misuse of the Veteran, 248 of the Veterans were engaged in mental health care; this number rose 54% to 382 at follow-up. CSO callers had at least one call with a coach and some had more than 20. For a separate subsample of 109 callers of Veterans with substance misuse who entered coaching, the rate of treatment rose a more modest 40%, or 35 to 49 Veterans in care. In these uncontrolled findings the initial treatment engagement rate of those who entered coaching was somewhat higher for those with substance misuse vs. no substance misuse (34% vs 26%). It does appear, however, that additional systematic strategies are needed for those Veterans with substance misuse problems. See the Appendix for CIC Manuals.

Preliminary feasibility test of the web-based delivery of CRAFT for PTSD

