The primary goal of the trial intervention will be a test of the feasibility of Coaching-CRAFT, CSO’s experience and engagement in the intervention, and within-subject estimates of changes in Veterans’ engagement in treatment. We will seek to enter 50 family member callers into a nonrandomized trial over 6 months. Each research-based telephone contact will be audio recorded for examination using the fidelity scale developed in months 1-4.

An additional goal is to compare the outcome in the trial to a usual-care sample of at least 50 CIC callers that have not been offered Coaching-CRAFT, matched on the basis of the Veteran’s primary substance use problem(s), relationship of CSO to Veteran, contact time and co-habiting

status, Veteran age and gender, and race. We will select comparison cases from a several year time-frame to ensure an appropriate comparison.

The length of the active coaching of the CSO using the web-based CRAFT material is anticipated to last no longer than 6 months, but this will be determined by the treatment manual development phase. Additional assessments will occur at 6 and 12 months after study entry and will include the measures as detailed in the table (above). *At 12 months, we will ask the CSO to invite the Veteran to engage in the study and answer study questions about their symptoms, treatment, and the CSO's approach to them.* We will carefully assess the safety and risk to the CSO-Veteran relationship prior to making the decision to pursue this assessment. Working with the CSO, we will ask the CSO to ask the Veteran to be involved, including type of discussion between CSO and Veteran might be helpful, and ask the CSO to ask the Veteran to call the study staff (see Human Subjects).

Timeline

We anticipate the trial will begin in Year 1 with initial recruitment occurring from months 5-10. The trial will end in Year 2, month 22. Analyses of feasibility, satisfaction and treatment engagement will occur in months 19-24. After the formal participation in the trial, any caller who needs additional support or treatment referral will be referred to the CIC call center.

Data Analysis, Sample Size considerations, and intervention modification

Feasibility Outcomes

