We will examine CSOs ratings of the intervention with a criterion of at least 80% of those rating the intervention as helpful, leading to increased hopefulness and preparedness to help the Veteran, and that the intervention had helped the family overall. We will also examine the degree to which the subjective symptoms of distress (PHQ-9, subjective burden), decline over the Baseline, 6 month, and 12 month assessments, using a mixed methods model test of within-subjects change over time. We will compare the completion rates of the Coaching-CRAFT sample of CSOs with a sample of CSOs from the CIC QA data. "Completion" will mean at least 6 months of telephone coaching of 8+ calls. We will match CSOs receiving Coaching-CRAFT with the treatment as usual data (see above).

Intervention comparisons

In a key analysis we will also plan to test the proportion of the Veterans of the CSOs who entered treatment for substance misuse against the matched CSOs from the CIC QA data. We will use an intent-to-treat approach. Those CSOs lost to follow-up will be deemed intervention failures regarding the Veterans' engagement in treatment. We plan to use a basic test of difference between proportions in independent samples (a two sample z-test). To detect a difference between the rate of engagement in treatment using CIC QA data (i.e., 41%) and conservative outcomes drawn from the CRAFT RCTs (67%), the sample group needed to detect a difference with power of 80% in post-intervention treatment engagement outcomes, is $N = 45$, for each group [29]. Our intent-to-treat sample size of $N = 50$ exceeds this number.

Review of CSO and Veteran report: *Qualitative and treatment engagement reports*

We plan to conduct a systematic review of the responses to the post-intervention open-ended questions in order to modify the intervention as needed in preparation for a large RCT. In addition, we plan to assess the rate of Veteran inclusion in the study at 12 months, *the CSO report, the VHA report of Veteran treatment utilization, and the comparison of these different data sources.*

Considerations of alternative approaches

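### The usual-care comparators come from an open QA file with some outcomes already known, and no window, ratio or outcome-blind selection step is fixed; use every eligible caller, selected blind and frozen early

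*Combined protocol and SAP*

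**What the plan says.** Under Trial procedures: "An additional goal is to compare the outcome in the trial to a usual-care sample of at least 50 CIC callers". They are callers not offered Coaching-CRAFT, matched on seven variables: the Veteran's primary substance problem, relationship, contact time, co-habiting status, and the Veteran's age, gender and race. The cases are to come from a period of several years. No dates, ratio, matching algorithm or tie rule are given, and nothing says that selection is made without sight of outcomes.

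Under Intervention comparisons, the test of Veterans' treatment entry against these callers is called a key analysis. The method is "a basic test of difference between proportions in independent samples (a two sample z-test"). The sizing assumes 41% against 67% with "power of 80% in post-intervention treatment engagement outcomes", and the number needed "is $N = 45$, for each group". Alpha and sidedness are not stated.

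The Coaching Into Care section of Preliminary Studies already reports outcomes for "a separate subsample of 109 callers of Veterans with substance misuse who entered coaching": 35 Veterans in care at the start and 49 at follow-up. The Timeline puts recruitment in months 5-10 and the end of the trial in month 22, and adds: "Analyses of feasibility, satisfaction and treatment engagement will occur in months 19-24".

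**The concern.** In a non-randomised comparison with a historical control, choosing the control group does part of the work that randomisation would otherwise do. Here some outcomes exist before anyone chooses, and the rule for choosing is open in three ways: which years, how many callers, and which of several acceptable matches. Each choice can be reasonable in itself and still move the control rate by several points. No step in the plan prevents the set from being settled, or revised, after results have been seen.

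The second issue is efficiency. The comparators are existing records, so if more than 50 are eligible, a comparison sized at 50 against 50 is less precise than it could be. An effect estimate from this pilot is also likely to inform the large RCT that the plan says it prepares for.

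**Working it through.** **Inputs.** Control rate 41%, treated rate 67%, power 80%, z-test, 45 per group (Intervention comparisons). 50 treated and a minimum of 50 comparators (Trial procedures). 109 coached substance-misuse callers, 35 in care at the start and 49 at follow-up (Preliminary Studies). The number of eligible QA callers is not given, so pool sizes below are assumptions. The lowest, 74, is 109 - 35, the callers in that sample whose Veteran was not in care at the start.

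**1. The plan's own figure.** n per group = [z_a √(2p̄q̄) + z_b √(p1q1 + p2q2)]² / (p2 - p1)², with p̄ = 0.54, 2p̄q̄ = 0.4968, p1q1 + p2q2 = 0.2419 + 0.2211 = 0.4630 and (p2 - p1)² = 0.0676.
- One-sided 5%: (1.645 × 0.7048 + 0.8416 × 0.6804)² / 0.0676 = 3.000 / 0.0676 = 44.4, so 45. This matches.
- Two-sided 5%: (1.96 × 0.7048 + 0.8416 × 0.6804)² / 0.0676 = 3.819 / 0.0676 = 56.5, so 57.

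The stated 45 therefore corresponds to a one-sided 5% test, so both versions are shown below.

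**2. Precision with 50 treated and m comparators.** SE = √(0.2211/50 + 0.2419/m). SE0 = √(p̄q̄(1/50 + 1/m)), with p̄ = (50 × 0.67 + m × 0.41)/(50 + m). Power = Φ((0.26 - z_a SE0)/SE). For m = 50: SE = 0.0962, SE0 = 0.0997, and (0.26 - 1.96 × 0.0997)/0.0962 = 0.67, giving 74.9%.

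| m | 95% CI half-width (points) | Power, one-sided 5% | Power, two-sided 5% |
|---|---|---|---|
| 50 | 18.9 | 84.1% | 74.9% |
| 74 | 17.2 | 89.4% | 82.1% |
| 100 | 16.2 | 92.2% | 86.2% |
| 150 | 15.2 | 94.7% | 90.1% |

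With weights w, m is replaced by about (Σw)²/Σw², which is smaller than the head count, so these rows are upper limits.

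**3. How far the control rate can move.** As an illustration, take the 109 callers with 49 engaged. A blind random draw of 50 has mean 45.0% and SD √(50 × 0.4495 × 0.5505 × 59/108)/50 = 5.2 points; the exact 95% range is 34% to 56%. With 50 per group, the treated rate needed for |z| ≥ 1.96 moves with the control rate: 56% if the control is 36%, 66% if 46%, 74% if 54%.

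**4. Effect of choosing.** Simulation with no true effect: treated count from Binomial(50, 0.41), pool of N callers at 41%, five random sets of 50 drawn from the pool, and the lowest-rate set kept. The entries are false claims of benefit; for the two-sided test this is the upper tail only (nominal 2.5%).

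| Pool N | Mean control rate kept | One-sided 5%: one fixed set → lowest of five | Two-sided 5%: one fixed set → lowest of five |
|---|---|---|---|
| 74 | 36% | 4.8% → 11% | 2.6% → 6% |
| 109 | 35% | 4.9% → 13% | 2.7% → 7% |
| 150 | 34% | 4.9% → 14% | 2.7% → 8% |

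Using the whole pool, with nothing to choose, gives about 5% and 2.5-2.7% in every row.

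**The case against.** **Fifty is a minimum.** A reader might infer that the plan caps the comparators at 50 and so wastes free data. It does not: more are already permitted, and the 45 per group shows adequacy at equal sizes. This objection stands. What remains is that no ratio or rule says how many will be used.

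**The pool may be small.** Of the 109 callers, 74 were not in care at the start. If half of those concern Iraq or Afghanistan-era Veterans (the share reported for all calls, assumed to apply here), about 37 remain before the relationship and contact criteria. Against that, the plan estimates about 600 relevant callers a year and allows several years, though not all are coached or followed up. The precision gain is therefore conditional. The selection problem exists at any pool size that leaves a choice.

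**Matching limits the choice.** The simulation draws sets at random. A small illustrative run (600 repetitions, pool of 150, assumed category shares) with nearest matching on the seven variables gave 11.8% instead of 14.8% one-sided, and 6.3% instead of 7.5% two-sided. With so few repetitions this shows direction only: the problem shrinks but does not vanish.

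**Timing and intent.** A reader might infer from the month-19 analysis start that comparators will be picked after results are seen. The documents do not say when they are picked, and nothing suggests that anyone would keep a favourable set. The point is only that no step rules it out.

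**Intent-to-treat.** A reader might also infer that matching on seven variables would leave trial callers unmatched and break the intent-to-treat 50. The plan requires neither exact nor 1:1 matching, does not say that unmatched callers are dropped, and ties intent-to-treat to loss to follow-up. That inference is not supported.

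**Stakes.** Feasibility comes first, and the plan says that the pilot is not primarily a test of efficacy. This lowers the priority, but the same plan calls this comparison key.

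**Conclusion.** The concern holds as a missing safeguard with a cheap, better alternative. The comparator set is open in years, number and matching rule while some of its outcomes are known. Choosing the lowest of five sets would raise false claims of benefit from about 5% to 11-14% one-sided, or from about 2.7% to 6-8% two-sided. This assumes a true rate of 41% in both groups, pools of 74 to 150 and random sets; for five sets it is an upper limit, and it measures what the plan permits, not what anyone intends.

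The precision loss is real only if more than 50 callers are eligible. Two-sided power would then rise from 75% to 82% with 74 comparators, 86% with 100 and 90% with 150, less whatever weighting costs. These figures take the plan's 41% at face value. The substance-misuse QA callers were at 49/109 = 45%, where two-sided power is 60% with 50 comparators and 78% with 150. More comparators narrow the interval but do not remove confounding, nor the gap between QA follow-up at about 3 months and trial follow-up at 6 and 12 months.

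**What to change.** In Trial procedures, replace the minimum-of-50 sample with all QA callers in a fixed date window who meet the trial's entry criteria as far as QA records allow, including that the Veteran was not in treatment at first call. Choose the window from counts of eligible callers only. Match at variable ratio, or weight, to all 50 trial CSOs on the variables already listed, by a written algorithm, and use a variance that reflects the matching or weights. Build the set from an extract with the outcome fields removed. Freeze it at the end of recruitment (month 10): the first caller enters in month 5, so 6-month assessments start around month 11. State alpha and sidedness in the same paragraph.

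The cost is one protocol paragraph and some programming, with no enrolment. It depends on QA records holding the matching variables in usable form, which the documents do not confirm. The downside is that weighting is slightly harder to describe than pairs and lowers the effective sample size.

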Recruitment for the sample in the trial will occur within the regular workflow of the CIC call center. We have estimated that on a yearly basis approximately 600 callers to CIC are first degree relatives of an OEF-OIF-OND Veteran who has a primary difficulty with substance misuse, yielding 300 potential referrals for the 6 active recruitment months of the trial. Initial assessment and problem identification has typically been conducted by a CIC call responder in the first 1-3 calls, often involving consultation with a licensed supervisor. Potential participants include the following: 1) CSO is a sibling, spouse/ intimate partner, or parent of a US military Veteran who served in Iraq or Afghanistan since 2001, 2) by the report of the CSO the Veteran of interest has a substance abuse problem that has led to interpersonal, legal, occupational, and/or health related negative consequences, 3) the CSO reports that the Veteran is not currently receiving treatment for this problem, and 4) the CSO has contact 4+times/week and lives with or within 30 min. of the Veteran. Exclusion criteria include: 1) CSO has an SUD (Form 90, see Measures), 2) the Veteran is currently incarcerated, 3) the CSO has no computer or other device with Internet access able to view video content, and 4) the CSO or Veteran likely has a psychotic disorder (CSO report on the MINI) (see Measures). Potential participants will be presented the option of being involved in the research trial, and if interested, will be contacted by the research staff. If the CSO is interested after hearing more details the research staff will conduct the additional screening, consent procedures, and baseline assessment. *We will also engage Veterans in the study at two points. First, if/when the CSO indicates that the Veteran wants treatment, we will offer help to the Veteran in an initial telephone conversation. In this conversation we will ask to use their responses as research data. Second, we will ask the CSO at 12 months after the baseline to invite the Veteran to participate (see below).*

Measures.

Demographic information (from CSO). Age, gender, race, marital status, relationship of CSO to the Veteran, living status (i.e., with the Veteran), hours in contact per week, Veteran's military service details (branch, highest rank, combat deployments, National Guard/Reserve component vs. regular Army/Navy/Marines/Air Force), Veteran's age, race, marital status, and number of children.

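### The matched QA comparators are not required to meet the trial's exclusions or to have entered coaching, and matching cannot remove the volunteer selection of trial CSOs

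*Combined protocol and SAP*

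**What the plan says.** Trial procedures states this as an additional goal: "compare the outcome in the trial to a usual-care sample of at least 50 CIC callers that have not been offered Coaching-CRAFT, matched on the". The matching variables are the main substance problem, kinship, amount of contact and shared household, the Veteran's age and sex, and race. Comparators may be drawn from several years. No other condition on a comparator is stated.

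Trial CSOs enter under Sample and recruitment procedures. The start is ordinary call-center practice: "Initial assessment and problem identification has typically been conducted by a CIC call responder in the first 1-3 calls". The trial is then offered, and research staff contact those who are willing. After that, "If the CSO is interested after hearing more details the research staff will conduct the additional screening, consent procedures, and baseline assessment". The exclusions are a substance use disorder in the CSO, an incarcerated Veteran, no Internet device that can show video, and likely psychosis in either person. One inclusion criterion is that the Veteran is untreated for the substance problem.

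On the existing QA data, the call-center section reports that "CSO callers had at least one call with a coach and some had more than 20", and its outcome samples are callers who had begun coaching.

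Intervention comparisons calls the test of Veterans' entry into treatment a key analysis and specifies "a basic test of difference between proportions in independent samples (a two sample z-test"), with trial CSOs lost to follow-up counted as failures. Feasibility Outcomes compares completion (at least 6 months of coaching and 8 or more calls) with the same matched QA data.

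**The concern.** The two groups reach the denominator by different routes. A trial CSO has volunteered, been screened and consented. A comparator need only have called, not been offered Coaching-CRAFT, and match on the listed variables. A CSO's motivation and persistence plausibly influence whether the Veteran enters treatment, and they bear directly on whether the CSO completes 8 calls. None of the matching variables measures them.

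The team's own experience suggests that enrolment selects on concern. Preliminary Studies reports that about 19% of potentially eligible family members joined the web-course trial, and that most withdrawals were by people whose worry about the Veteran had faded during enrolment. The plan expects less of this among CIC callers. But continuing to be concerned is not the same as agreeing to research and passing a screen.

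At stake is whether a higher engagement or completion rate under Coaching-CRAFT can be read as an effect of the intervention when the later RCT is planned.

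**Working it through.** **1. Entry conditions side by side**

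| Condition | Trial CSO | QA comparator, as stated |
|---|---|---|
| Intake calls | Yes, usual CIC workflow | Not stated; usual workflow |
| Entered coaching | Yes, by design | Not stated; true of the QA samples already reported |
| Substance problem, kinship, contact, shared household | Eligibility criteria | Matched |
| Veteran untreated at entry | Required | Not stated |
| CSO substance use disorder | Excluded (Form 90) | Not stated |
| Likely psychosis, CSO or Veteran | Excluded (MINI) | Not stated |
| Veteran incarcerated | Excluded | Not stated; contact match makes it unlikely |
| Internet device | Required | Not stated; nearly all callers have access |
| Accepted a research offer and consented | Required | Not applicable, never offered |

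The differences that matter are the volunteer step, CSO substance use disorder, psychosis and baseline treatment status. The z-test adjusts for none of them.

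**2. The plan's own sample size**

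Inputs from Intervention comparisons: 41% against 67%, power 80%, stated N = 45 per group. Neither alpha nor sidedness is given; I assume 5% and try both.

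n = [z_α √(2p̄(1−p̄)) + z_β √(p₁(1−p₁) + p₂(1−p₂))]² / (p₂−p₁)²

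with p̄ = 0.54, √0.4968 = 0.7048, √0.4630 = 0.6804 and z_β = 0.842.

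- One-sided: (1.645 × 0.7048 + 0.842 × 0.6804)² / 0.0676 = 44.4, so 45.
- Two-sided: (1.960 × 0.7048 + 0.842 × 0.6804)² / 0.0676 = 56.5, so 57.

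The stated 45 is reproduced one-sided only, so both versions are shown next.

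**3. Illustration of a selection shift**

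Take 50 per group, a comparator rate of 41%, no intervention effect, and a trial rate higher by an assumed b through selection alone. The documents give no value for b.

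P(significant, favouring Coaching-CRAFT) = Φ[(b − z_α·SE₀)/SE₁], where SE₀ = √(2p̄(1−p̄)/50) and SE₁ = √((p_c(1−p_c) + p_t(1−p_t))/50).

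- b = 5 points: SE₀ = 0.0992, SE₁ = 0.0990; two-sided Φ(−1.46) = 7%; one-sided Φ(−1.14) = 13%.
- b = 10 points: SE₀ = 0.0997, SE₁ = 0.0992; two-sided Φ(−0.96) = 17%; one-sided Φ(−0.65) = 26%.
- b = 0: 2.5% and 5%.

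**4. A force in the other direction**

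In the QA substance-misuse sample, 35/109 = 32% of Veterans were in care at the start and 49/109 = 45% at follow-up. If none left care, new entry among the untreated is (49−35)/(109−35) = 14/74 = 18.9%. Suppose that rate applies to both groups, and that a share g of comparators was already in care and is counted as engaged. The comparator rate is then g + (1−g) × 0.189.

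| Share already in care | Comparator rate | Trial minus comparator, b = 10 | b = 20 |
|---|---|---|---|
| 0 | 18.9% | +10.0 | +20.0 |
| 0.10 | 27.0% | +1.9 | +11.9 |
| 0.32 | 44.9% | −16.0 | −6.0 |

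So the sign of the total bias depends on a criterion that the plan does not state for comparators. The plan also does not say whether its loss-as-failure rule applies to QA callers. If it does not, that too lowers the trial rate relative to theirs.

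**The case against.** The best defence is that the comparators are close to the right people already. They are a matched usual-care sample, intake is routine for every caller, and the reported QA outcomes come from callers who had entered coaching. Comparing rates of 8 or more calls makes little sense for anyone else. This stands to the extent that a reader who infers that volunteers are compared with all comers goes too far. What remains is that the selection rule in Trial procedures does not carry the coaching condition over or apply the exclusions.

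Three other stronger readings are not supported:

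- **Incarcerated Veterans or callers without Internet distort the comparison.** Matching on contact and shared household makes the former rare, and the plan reports near-universal Internet access among callers.
- **Enrolling 50 of 300 potential referrals (17%) measures how selective volunteering is.** The 50 is a recruitment target, and the 300 are counted before the contact, proximity and untreated criteria. People may go unenrolled because they are ineligible or because the target has been reached.
- **The comparison as a whole favours Coaching-CRAFT.** Step 4 of the working shows that it could go either way.

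It is also fair to say that the plan discloses an uncontrolled design aimed at feasibility and proof of concept, not efficacy. That limits the consequence. But the same plan calls this comparison a key analysis and bases its sample-size justification on it.

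**Conclusion.** The concern holds in a limited form. The comparator rule omits the trial's exclusions (chiefly CSO substance use disorder and likely psychosis) and does not state that comparators must have entered coaching. Volunteer selection is left unaddressed by the matching and uncorrected by the test. This component plausibly favours Coaching-CRAFT for both engagement and completion.

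Its size is not derivable from the documents. The figures of 7% and 17% (13% and 26% one-sided) only translate assumed shifts of 5 and 10 points into error rates, taking the plan's 41% as given. The net direction of bias is undetermined, and two opposing biases of unknown size do not make the comparison sound. Correcting treatment status alone would leave volunteer selection without the counterweight shown in step 4.

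**What to change.** In Trial procedures:

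1. Restrict comparators to callers who completed intake, accepted coaching and had at least one coaching call.
2. Apply every trial inclusion and exclusion criterion that QA records hold, including that the Veteran was untreated at entry, and list the criteria that they do not hold.
3. Report QA engagement rates for callers who appeared eligible, were offered the trial and declined, beside the rate in the matched comparators. Decliners cannot serve as comparators, since they were offered Coaching-CRAFT, and their eligibility is known only as far as intake shows it. The table is therefore descriptive.
4. In Intervention comparisons, say whether the loss rule also covers comparators, and describe the between-group difference as subject to volunteer selection.

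The cost is a tighter query on existing records and one extra table. The matching pool becomes smaller, which the several-year time frame partly offsets. Some items will be incompletely recorded, notably psychosis and CSO substance use disorder, because the trial measures these with study instruments that QA records may lack. The restriction reduces the selection difference but does not remove it, because no query can identify which comparators would have volunteered.

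### The key test compares Veterans not in treatment at entry with usual-care cases who may already be in treatment at first call

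*Combined protocol and SAP*

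**What the plan says.** Sample and recruitment procedures makes it an entry condition that "the CSO reports that the Veteran is not currently receiving treatment for this problem". By family-member report, then, no trial Veteran is in treatment at baseline.

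Trial procedures takes as its comparison group a "usual-care sample of at least 50 CIC callers that have not been offered Coaching-CRAFT". The selection rule for these cases is that they be "matched on the basis of the Veteran’s primary substance use problem(s), relationship of CSO to Veteran, contact time and co-habiting" (whether the two live together); the list then adds the Veteran's race, gender and age. The Overview gives a shorter list: type of substance misuse and demographic variables. Neither list includes treatment status at first call, and no other section adds it.

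Intervention comparisons names as a key analysis one that will "test the proportion of the Veterans of the CSOs who entered treatment for substance misuse against the matched CSOs from the CIC QA data", using an unadjusted two-sample z-test. The only sample-size calculation rests on this test. It sets "the rate of engagement in treatment using CIC QA data (i.e., 41"%) against 67% and arrives at 45 per group for 80% power.

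The Preliminary Studies section on the call center reports that, among 109 callers about substance misuse, "the rate of treatment rose a more modest 40%, or 35 to 49 Veterans in care". The QA follow-up is short: "Within about 3 months of first calling, the treatment engagement of the Veteran" is said to rise modestly. In the trial, "Additional assessments will occur at 6 and 12 months after study entry".

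**The concern.** Being in treatment at the start is almost the outcome itself, so matching on age, substance or relationship cannot balance it. One group starts with nobody in treatment; the other may start with about a third. Intervention comparisons does not say how a comparator already in treatment is counted, and both ways of counting distort the test:

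- **Reading A, in care at follow-up counts as engaged.** The comparator is credited with treatment that preceded the call, and the test is biased against Coaching-CRAFT.
- **Reading B, only new entry counts.** Comparators already in treatment stay in the denominator but cannot succeed, and the test is biased in favour of Coaching-CRAFT.

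The difference in follow-up windows adds to the problem. A longer trial window raises the trial's rate, which partly offsets A and adds to B.

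At stake is whether the result can tell the team if Coaching-CRAFT does better than usual coaching, before the RCT the plan anticipates. The Overview justifies having no control arm partly by the availability of QA data, and that argument needs comparable QA cases.

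**Working it through.** **The plan's own figure.** With p1 = 0.41, p2 = 0.67 and mean 0.54, the pooled-variance formula is n = [z_α√(2·0.54·0.46) + 0.842·√(0.41·0.59 + 0.67·0.33)]² / 0.26².
- One-sided 5% (z = 1.645): 44.4, so 45 per group. This matches the plan.
- Two-sided 5% (z = 1.960): 56.5, so 57 per group.

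The stated 45 therefore implies a one-sided 5% test. The plan states neither alpha nor sidedness.

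**Where 41% could come from.** The source is not given. In the QA sample without substance misuse, 382/939 = 40.7%. Pooling both QA samples gives (382 + 49)/(939 + 109) = 431/1048 = 41.1%. Both are proportions in care at follow-up and include Veterans already in care at the start, which points towards reading A.

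**Rates from the substance-misuse QA sample.**
- In care at start: 35/109 = 32.1% (the text also gives 34%).
- In care at follow-up: 49/109 = 45.0%.
- Net new entry among those not in care at start: (49 − 35)/(109 − 35) = 14/74 = 18.9%. This is a minimum. If 5 or 10 of the 35 left care, new entries are 19/74 = 25.7% or 24/74 = 32.4%.
- New entries over the unrestricted denominator: 14/109 = 12.8%, 19/109 = 17.4% or 24/109 = 22.0%.

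**Test behaviour with no true effect.** The probabilities below come from exact binomial enumeration of the pooled z-test with 50 per group. They assume that all 35 were in substance treatment and that the roughly 3-month QA rate applies to the trial.

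| Number of the 35 who left care | Trial rate | A: comparator 45.0%, P(declared worse), two-sided 5% | B: comparator rate | B: P(false better), two-sided / one-sided 5% |
|---|---|---|---|---|
| 0 | 18.9% | 0.81 | 12.8% | 0.14 / 0.20 |
| 5 | 25.7% | 0.53 | 17.4% | 0.17 / 0.26 |
| 10 | 32.4% | 0.25 | 22.0% | 0.22 / 0.32 |

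With equal true rates, the chance of a false better result would be about 0.025 two-sided or 0.05 one-sided, and the chance of a false worse result about 0.025 two-sided.

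In the first row, the gap under A is 18.9 − 45.0 = −26 points. The effect the study is sized for is 67 − 41 = 26 points, so the artefact is as large as the target.

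**Longer trial follow-up under A.** If no-effect entry reached 30% or 35% by the trial visits, P(declared worse) is 0.34 or 0.18.

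**Power at a true 67%, 50 per group.** Against 45.0% it is 0.63 two-sided or 0.71 one-sided. Against restricted comparators it is 0.95 / 0.97 at 32.4%, 0.99 / above 0.99 at 25.7%, and above 0.99 either way at 18.9%.

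**The case against.** The strongest counter-argument is that this is a pilot. The plan says its primary focus is feasibility rather than efficacy, and the helpfulness criterion, the symptom analyses and the within-subject estimates use no comparator. That stands and limits the reach of the problem. It does not remove it, because the plan itself calls this comparison key and draws its sample size from it.

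A second argument is that entering treatment implies not yet being in it, and that the matching list may be meant to apply on top of the trial's eligibility criteria. That may be the intention, but the plan does not say so, and followed as written the rule lets in Veterans already in treatment.

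Third, the 81% is the extreme of the range. It needs a two-sided test, nobody leaving care, all 35 in substance treatment, and a 3-month rate carried to later visits. This is fair. Under the one-sided test implied by N = 45, a verdict of worse cannot occur and the cost is missed benefit. The term 'in care' is also undefined for the 109, and a Veteran in mental health care only would still meet the trial's criterion. If only 10 or 17 of the 35 were in substance treatment (assuming all stayed and all 14 net entries were substance treatment), P(declared worse) under A is 18% or 37%. False benefit under B is then 4% or 6% two-sided (7% or 9% one-sided), close to nominal.

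Finally, a significant benefit under A might be called conservative. That is not safe while the trial's outcome is read at 6 or 12 months and the QA outcome at about 3.

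**Conclusion.** The concern holds and should be fixed before comparison cases are drawn. Entry criteria and comparator selection differ on baseline treatment status, and the plan's own counts show that this affects about a third of substance-misuse callers. The unadjusted test is then biased under either way of counting, and because the outcome is not fully defined, even the direction is open.

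The size is conditional. With all 35 in substance treatment and up to 10 leaving care, a false verdict against Coaching-CRAFT has probability 25% to 81% under A (two-sided), and a false benefit 14% to 22% two-sided or 20% to 32% one-sided under B. At the planned 67%, power under A is 63% two-sided or 71% one-sided, below the 80% intended. Under A the gap nearly closes only if about 19 of the 35 left care, since (14 + 19)/74 = 44.6%. The bias is smaller if some were in mental health care only. The aims that use no comparator are unaffected.

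**What to change.** - **Trial procedures:** require comparison cases to meet the trial's inclusion criteria at first call, in particular that the Veteran is not in treatment for the substance problem. If QA records cannot separate substance treatment from other care, say so, and report the comparison with and without Veterans in any care at first call.
- **Intervention comparisons:** define the outcome in both groups as new entry into substance-misuse treatment within the same follow-up window. Record the date of first entry in the trial so that it can be counted at the QA window.
- **Sample size:** replace 41% with the new-entry rate from the restricted QA records (about 19% net from the published counts, higher if some Veterans left care). Restate power with alpha and sidedness.

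The cost is one eligibility sentence, one outcome definition and one filter. The QA data record care status at start and follow-up, though perhaps not specifically for substance treatment. The eligible QA pool shrinks by about a third (74 of 109 remain), which selection over several years can probably absorb. Counting at the QA window leaves later entries out of this comparison. That is the more debatable part; the later entries can still be reported within the trial group.
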